- When several toxicities with different grades of severity occur at the same time, appropriate action should be made according to the highest grade observed.
- If, in the opinion of the investigator, a toxicity is considered to be due solely to MGC018 and is of sufficient grade to warrant treatment delay, therapy should be delayed and omitted until resolution of toxicity.
- If, in the opinion of the investigator, a toxicity attributed to MGC018 is of sufficient grade to warrant permanent discontinuation of therapy, therapy should be permanently discontinued.

For patients who require a dose-reduction, the first reduction would be to 1.5 mg/kg every 28 days with a second reduction to 1.0 mg/kg every 28 days, as needed (**Table 4**).

Table 4. Dose levels of MGC018

| Dose levels | MGC018 |
|-------------------------|---------------|
| Level 1 (starting dose) | 2.0 mg/kg Q4W |
| Level -1 | 1.5 mg/kg Q4W |
| Level -2 | 1.0 mg/kg Q4W |

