| Neutropenia, Grade 1 or 2 | 
 • No specific therapy required • MGC018 should not be given to participants with neutrophil counts ≤ 1500 cells/mm³ • Consider dose reduction of MGC018 |
| Neutropenia, Grade 3 | 
 • Hold MGC018 until recovery to \leq grade 1 • Monitor neutrophil counts weekly until recovery to \leq grade 1 • Discontinue MGC018 if not recovered to \leq grade 1, within 21 days • Restart MGC018 if recovered to \leq grade 1 within 21 days. • On resuming MGC018, reduce dose by one dose level after first and second occurrences • Discontinue MGC018 after third occurrence |
| Neutropenia, Grade 4 | 
 • Hold MGC018 until recovery to \leq grade 1 • Monitor neutrophil counts weekly until recovery to \leq grade 1 • Discontinue MGC018 if not recovered to \leq grade 1, within 21 days • Restart MGC018 at one or two level dose reduction if recovered to \leq grade 1 within 21 days. • On resuming MGC018 reduce dose by two dose levels after first occurrence • Discontinue MGC018 after second occurrence |
| Thrombocytopenia, Grade 1 | 
 • No specific therapy required • Consider dose reduction of MGC018 |

| | |
|-----------------------------------|--|
| Thrombocytopenia, Grade 2 or 3 | 
 • Hold MGC018 until recovery to \leq grade 1 • Monitor platelet counts weekly until recovery to \leq grade 1 • Restart MGC018 with one level dose reduction if recovered to \leq grade 1 • Reduce dose by one dose level on resumption after second and third occurrences • Discontinue MGC018 after fourth occurrence • Discontinue MGC018 if not recovered to \leq grade 1 within 21 days. |
| Thrombocytopenia, Grade 4 | 
 • Hold MGC018 until recovery to \leq grade 1 • Monitor platelet counts weekly until recovery to \leq grade 1 • Restart MGC018 with one or two level dose reduction if recovered to \leq grade 1 • Discontinue MGC018 if not recovered to \leq grade 1 within 21 days. • On resuming MGC018 reduce dose by two dose levels after first occurrence • Discontinue MGC018 after second occurrence |
| Anemia, Grade 1 | 
 • No specific therapy required |
| Anemia, Grade 2 | 
 • Consider iron replacement therapy, erythropoiesis stimulating agent |

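### Both grade 4 cytopenia cells in Table 13 carry two restart rules that disagree, and the dose-reduction text around them has no floor, one ambiguous row and an outright contradiction

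*Combined protocol and SAP*

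**What the plan says.** Section 4.2.3.1 and its Table 4 set the dose levels. Treatment starts at 2.0 mg/kg every 28 days, and "the first reduction would be to 1.5 mg/kg every 28 days with a second reduction to 1.0 mg/kg every 28 days". No lower level is listed, and the text does not say what happens when one would be needed.

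In Table 13 (Section 4.2.3.2) the relevant cells read:

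- Neutropenia, grade 4: "Restart MGC018 at one or two level dose reduction if recovered to" grade 1 or lower within 21 days; then "On resuming MGC018 reduce dose by two dose levels after first occurrence"; then "Discontinue MGC018 after second occurrence".
- Thrombocytopenia, grade 4: "Restart MGC018 with one or two level dose reduction if recovered to" grade 1 or lower, with discontinuation if that takes more than 21 days, followed by the same two-level line and the same stop after a second event.
- Thrombocytopenia, grade 2 or 3: "Restart MGC018 with one level dose reduction if recovered to" grade 1 or lower; then "Reduce dose by one dose level on resumption after second and third occurrences"; then "Discontinue MGC018 after fourth occurrence".

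Two other places bear on the restart dose. The opening paragraph of Section 4.2.3.2 allows a general restart at an unchanged dose once an event has resolved to grade 1 or lower. The last sentence of Section 4.2.2 rules out any modification of the MGC018 dose, directly after a sentence that sends the reader to dose-modification guidelines in a Section 4.3.3 and an Appendix 4.

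**The concern.** A restart dose after a grade 4 cytopenia should be a single number that every site reads the same way. Here each grade 4 cell gives a permissive rule and a mandatory rule for the same event. A site that relies on the permissive line can restart at 1.5 mg/kg and breach the mandatory line beside it.

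What is at stake is patient safety and the readability of the safety data. Section 5.1.1 lists myelosuppression among the risks of MGC018, safety is a secondary objective (Section 2.2), and the trial runs at several sites with at most 17 patients. Section 9.2 does not allow prospective requests to deviate, so a site cannot settle an unclear cell by asking for a waiver.

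**Working it through.** **Step 1. Reductions available.** Table 4 lists three levels: 2.0, 1.5 and 1.0 mg/kg. Reductions below the start = 3 − 1 = 2, which agrees with the first and second reductions named in Section 4.2.3.1. As fractions of the starting dose, 1.5/2.0 = 0.75 and 1.0/2.0 = 0.50.

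**Step 2. Grade 4 cells.** Treatment stops after the second occurrence, so the first is the only one with a restart. Both restart lines therefore govern the same event.

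| Dose at the event | One level down | Two levels down |
|---|---|---|
| 2.0 mg/kg | 1.5 mg/kg | 1.0 mg/kg |
| 1.5 mg/kg | 1.0 mg/kg | no such level |
| 1.0 mg/kg | no such level | no such level |

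From 2.0 mg/kg the permissive line allows 1.5 or 1.0, and the mandatory line requires 1.0. The one dose that meets both is 1.0 mg/kg.

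**Step 3. Comparison with other grade 4 rows.** Seven other rows have the two-level reduction after a first event and a stop after the second, with no one-level option: transaminases (Table 6), bilirubin (Table 7), diarrhea or colitis (Table 8), dermatologic (Table 9), nephritis (Table 10), hyperthyroidism (Table 11) and musculoskeletal (Table 18). The conflict between two lines is specific to Table 13. The missing step from 1.5 or 1.0 mg/kg is not: it arises in all of these rows because Table 4 has no floor rule. The same gap affects one-level steps from 1.0 mg/kg, for example after grade 3 neutropenia, palmar-plantar erythrodysesthesia or an effusion. A patient can reach 1.5 mg/kg by ordinary routes, such as palmar-plantar erythrodysesthesia or a first grade 3 neutropenia.

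**Step 4. Grade 2–3 thrombocytopenia.** The restart line is not tied to any particular occurrence.

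| Reading | After event 1 | After event 2 | After event 3 | Reductions |
|---|---|---|---|---|
| Restart line applies at the first event | 1.5 | 1.0 | no such level | 1 + 2 = 3 |
| Restart line does not apply at the first event | 2.0 | 1.5 | 1.0 | 0 + 2 = 2 |

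The second reading fits Table 4. Six grade 2 rows follow that pattern (Tables 6, 7, 9, 10, 11 and 18), but each says expressly that no reduction is needed after the first event. This row has no such statement and carries a reduction line instead.

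**Step 5. Section 4.2.2 against the rest.** Its ban on dose modification cannot stand with Table 4, with the management tables, with the hematologic text that has blood counts decide whether the dose needs modifying, or with the sentence just before it. The Section 4.3.3 and Appendix 4 named in that sentence are not in the table of contents; the guidelines are in Section 4.2.3.

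**Step 6. What is not affected.** The two-stage design continues with at least 1 response in 9 and rejects with at least 3 in 17. P(reject) = Σ (x = 1 to 9) C(9,x) p^x (1−p)^(9−x) × P(Bin(8,p) ≥ 3 − x). At p = 0.05 this is 0.0466 (stated 4.7%), and at p = 0.25 it is 0.8122 (stated 81.2%). Both figures reproduce, and neither involves the restart rules.

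**Step 7. Frequency.** Section 3.3.1 reports increased neutropenia at 3.0 mg/kg every 21 days. That is 3.0/3 = 1.0 mg/kg per week, against 2.0/4 = 0.5 here, a ratio of 2. It cannot be carried over as a rate for this trial.

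**The case against.** The strongest answer is that the grade 4 cells have a workable solution. At the starting dose 1.0 mg/kg complies with both lines, and it is also what seven other grade 4 rows require. That stands, and it limits the point. A reader might infer that 1.5 and 1.0 mg/kg are equally compliant; they are not, because 1.5 mg/kg breaks an explicit line. The defect is that the cell also invites the non-compliant dose.

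The phrase about one or two levels may also have been meant for a patient already at 1.5 mg/kg, who has one level left. That is plausible, but the protocol does not say so, the two-level line has no such exception, and a patient at 1.0 mg/kg is still not covered. A reader might treat the missing step as a fault of Table 13; it belongs to Table 4 and is shared by other tables. Section 4.5.1 already lets the investigator stop treatment for intolerable toxicity or in the patient's best interest, which softens the practical effect but sets no dose.

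On thrombocytopenia, a reader might conclude that the plan orders an impossible third reduction. That follows on only one of two readings, and only at a third recovered event within at most 8 cycles. The row is ambiguous, and the documents do not show that the impossible step was intended.

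The same-dose restart in the opening of Section 4.2.3.2 is permissive and general, so it competes only weakly with row-specific doses. It still does not say that the tables take precedence.

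**Conclusion.** The point holds as an internal inconsistency in the dosing rules. The two grade 4 cells each contain two rules that disagree for the only event with a restart: from 2.0 mg/kg, 1.5 mg/kg (75% of the starting dose) is permitted by one and ruled out by the other, and 1.0 mg/kg (50%) meets both. Separately, Table 4 has no floor, so the required two-level step exists from 1 of the 3 dose levels in any table that calls for it. The grade 2–3 thrombocytopenia row needs one stated rule, and the ban in Section 4.2.2 is wrong as written.

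This rests only on the wording of the protocol. No event rate is assumed, because the readable text gives none for 2.0 mg/kg every 28 days. A reader might infer a threat to the primary analysis; there is none, since type I error, power and sample size do not depend on these rules. The correction is worth making because it fixes a rechallenge dose after a severe event at little cost.

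**What to change.** 1. In both grade 4 cells of Table 13, delete the wording that allows one or two levels. Keep a two-level reduction after the first occurrence if the event recovers to grade 1 or lower within 21 days, and discontinuation after the second.
2. Beside Table 4, add a floor that serves every table: the lowest dose is level −2 (1.0 mg/kg); a two-level reduction from level −1 goes to level −2; a patient at level −2 who needs a further reduction discontinues MGC018.
3. In the grade 2–3 thrombocytopenia row, have the sponsor state one rule. Either there is no reduction after the first occurrence, one level after each of the second and third, and a stop after the fourth; or there is one level after each of the first and second, and a stop after the third. Both fit Table 4. The choice is clinical, and the documents do not favor one.
4. In Section 4.2.2, delete the sentence that forbids dose modification and point the preceding sentence to Section 4.2.3. In the opening of Section 4.2.3.2, limit the same-dose restart to events for which no table specifies a reduction.

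The downside is that some patients restart at 1.0 instead of 1.5 mg/kg, or stop earlier. The cost is one protocol amendment, with IRB approval and submission to regulatory authorities as locally required (Section 9.3). It needs no new procedures and no change in sample size.

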| Dermatologic event, Grade 4 | 
 • Initiate oral corticosteroids (oral prednisone 1 to 2 mg/kg/day) • Evaluate patient for use of concomitant medications or herbal supplements that may exacerbate skin toxicity • Consider obtaining a skin biopsy if possible diagnosis of SJS or TEN. If possible, refer to specialized care center for clinical management. Cyclosporine and/or IV immunoglobulin may be considered for management of SJS or TEN. |

| | |
|--|---|
| | 
 • Consideration should be given to start IV corticosteroids (methylprednisolone 1 to 2 mg/kg/day) for grade 4 dermatologic toxicities with tapering on resolution to <grade 2 over 30 days. • If SJS or TEN are confirmed, permanently discontinue MGC018 • On resuming MGC018 reduce dose by two dose levels after first occurrence • Discontinue MGC018 after second occurrence |
|--|---|

SJS=Stevens-Johnson Syndrome, TEN=toxic epidermal necrolysis

RENAL EVENTS

Immune-related nephritis is a potential risk with MGC018. Eligible patients must have adequate renal function. Renal function, including serum creatinine, should be monitored throughout study treatment. Patients with abnormal renal function should be evaluated and treated for other more common etiologies (including prerenal and postrenal causes, and concomitant medications such as non-steroidal anti-inflammatory drugs).

Patients with signs and symptoms of nephritis, in the absence of an identified alternate etiology, should be treated according to the guidelines in Table 10.

Table 10. Management Guidelines for Nephritis

| Event | Management |
|--------------------|---|
| Nephritis, Grade 1 | 
 • Continue MGC018 • No specific therapy required • Close monitoring of renal function |
| Nephritis, Grade 2 | 
 • Hold MGC018 • Consider nephrology consultation and renal biopsy to confirm interstitial nephritis. • Consider initiating treatment with corticosteroids equivalent to 1–2 mg/kg/day oral prednisone per day, dose divided twice daily. • Taper corticosteroids over 4 weeks or as clinically indicated. • Resume MGC018 at next scheduled dose if nephritis resolves to \leq grade 1 within 21 days with or without treatment • No dose reduction required after first occurrence • On resuming MGC018, reduce dose by one dose level after second and third occurrences • Discontinue MGC018 after fourth occurrence |

| | |

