|--------------------|--|
| Nephritis, Grade 3 | 
 • Consider hospitalization, nephrology consultation, and renal biopsy to confirm interstitial nephritis. • Initiate treatment with corticosteroids equivalent to 2–4 mg/kg/day IV methylprednisolone divided twice daily. Taper corticosteroids over 4 weeks or as clinically indicated. • On resuming MGC018, reduce dose by one dose level after first and second occurrences • Discontinue MGC018 after third occurrence |
| Nephritis, Grade 4 | 
 • Treat as grade 3 • On resuming MGC018 reduce dose by two dose levels after first occurrence • Discontinue MGC018 after second occurrence |

ENDOCRINE EVENTS

Endocrine events are a potential risk with MGC018.

Thyroid disorders may occur at any time during treatment with MGC018. Monitor participants for changes in thyroid function per protocol and as indicated based on clinical evaluation and for clinical signs and symptoms of thyroid disorders. Isolated hypothyroidism may generally be managed with replacement therapy without treatment delay and without corticosteroids.

Management guidelines for endocrine events are provided in Table 11.

Table 11. Management Guidelines for Endocrine Events

| Event | Management |
|-----------------------------|---|
| Hyperthyroidism, Grade 1 | 
 • Continue MGC018 • No specific therapy required |
| Hyperthyroidism, Grade 2 | 
 • Hold MGC018 • Consider starting oral corticosteroid therapy. • Short course of corticosteroid such as methylprednisolone 1 to 2 mg/kg IV (or equivalent) divided twice daily. • Resume MGC018 if corticosteroid if corticosteroid dose is reduced to ≤ 10 mg prednisone or equivalent per day and stable on hormone replacement therapy (if necessary). • No dose reduction required after first occurrence • On resuming MGC018, reduce dose by one dose level after second and third occurrences • Discontinue MGC018 after fourth occurrence |

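### The grade 2/3 thrombocytopenia row orders three dose reductions where Table 4 provides two, and the visible protocol has no rule for a reduction due at 1.0 mg/kg

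*Combined protocol and SAP*

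**What the plan says.** **The ladder.** Section 4.2.3.1 says that "the first reduction would be to 1.5 mg/kg every 28 days with a second reduction to 1.0 mg/kg every 28 days, as needed". Table 4 lists the same levels: 2.0 mg/kg (Level 1), 1.5 (Level -1) and 1.0 (Level -2). Section 3.3.1 repeats the two steps and refers to the investigator's brochure for details.

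**The row.** For grade 2 or 3 thrombocytopenia, Table 13 (Section 4.2.3.2) says "Restart MGC018 with one level dose reduction if recovered to" grade 1 or better, without tying this to any particular occurrence. The next bullet says "Reduce dose by one dose level on resumption after second and third occurrences". Discontinuation follows the fourth occurrence, or failure to recover within 21 days.

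**Comparable rows.** Six grade 2 rows elsewhere (Tables 6, 7, 9, 10, 11 and 18) also reduce after the second and third occurrences and stop after the fourth. Each of them also states "No dose reduction required after first occurrence". The thrombocytopenia row has no such line. The grade 3 neutropenia row in Table 13 says "On resuming MGC018, reduce dose by one dose level after first and second occurrences" and stops after the third.

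**Grade 4 hematologic rows.** For neutropenia the text is "Restart MGC018 at one or two level dose reduction if recovered to" grade 1 or better; for thrombocytopenia it is "Restart MGC018 with one or two level dose reduction if recovered to" grade 1 or better. Both rows also say "On resuming MGC018 reduce dose by two dose levels after first occurrence".

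**Section 4.2.2.** This section says that dose modification of the study drug is not allowed. It sends the reader to a Section 4.3.3 and an Appendix 4 for modification guidance. Neither is in the visible text, and the contents pages list no Section 4.3.3 and only three appendices.

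**The concern.** A dose-modification table should give every site a dose, or a stop, at each permitted restart. The grade 2/3 thrombocytopenia row appears to order more reductions than the ladder holds while still telling the site to resume treatment. At that point the site must choose for itself among staying at 1.0 mg/kg, going lower and stopping.

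The same question arises whenever a reduction falls due at the lowest level, because all toxicities share one ladder. In the two grade 4 hematologic rows, two sites could both follow the protocol and restart the same kind of patient at different doses.

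What is at stake is safe and uniform re-dosing after drug-related toxicity in a multi-center trial. The response-rate test is not affected.

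**Working it through.** **Inputs.** Ladder from Table 4: 2.0, 1.5, 1.0 mg/kg, one infusion per 28-day cycle, at most 8 cycles (Section 3.1.1). Occurrence rules from Tables 10 and 13. For the earliest case, assume that qualifying events follow infusions 1, 2 and 3, that each recovers by the next dose, and that no other toxicity has caused a reduction.

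**The plan's own figure.** Reductions available: 2.0 → 1.5 → 1.0 is 2 steps, as Sections 3.3.1 and 4.2.3.1 state.

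**Grade 2/3 thrombocytopenia as written.** Reductions ordered = 1 (at restart) + 1 (second occurrence) + 1 (third occurrence) = 3. Restarts before the stop rule = 4 − 1 = 3.

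| Restart after occurrence | Earliest infusion | Row as written | Restart bullet overridden at first occurrence | Grade 3 neutropenia rule |
|---|---|---|---|---|
| 1 | 2 | 1.5 | 2.0 | 1.5 |
| 2 | 3 | 1.0 | 1.5 | 1.0 |
| 3 | 4 | no defined dose | 1.0 | discontinued |

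The row as written needs 3 steps and the ladder has 2. The fourth column fits the ladder, but only by setting aside the unqualified instruction to restart one level down.

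**Across toxicities.** Suppose a one-level event follows infusion 1, so infusion 2 is at 1.5 mg/kg (Level -1). A first grade 4 nephritis then follows infusion 2. Table 10 orders two levels down on resuming, and one level remains. Infusion 3 has no defined dose.

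**Grade 4 hematologic rows.** From 2.0 mg/kg, one level gives 1.5 and two levels give 1.0. One bullet permits either dose and the other requires 1.0. The other seven grade 4 rows that carry a reduction (Tables 6, 7, 8, 9, 10, 11 and 18) say two levels only.

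**Does another rule settle it?**
- The opening of Section 4.2.3.2 lets treatment restart at the same level after a serious or grade 3/4 event. It does not cover a non-serious grade 2 event, and it conflicts with the reduction that the row orders. Its mandatory stop depends on a delay of more than 8 weeks.
- Sections 4.2.3.1 and 4.5.1 allow the investigator to stop treatment, but neither mentions the lowest dose level.
- Section 4.2.2 adds a conflict and supplies no rule.

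**Side check on the Simon design.** Stage 1 has 9 patients and continues with at least 1 response; stage 2 adds 8; the null is rejected with at least 3 responses in 17. P(reject) = Σ over x = 1 to 9 of P(X = x)·P(Y ≥ 3 − x), with X ~ Bin(9, p) and Y ~ Bin(8, p). At p = 0.05 this is 0.0466 (stated 4.7%); at p = 0.25 it is 0.8122 (stated 81.2%). Both figures reproduce, and no dosing rule enters them.

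**The case against.** The best defence is that the consequence is small. The row requires recovery to grade 1 or better, weekly counts, and a stop if recovery takes longer than 21 days. Investigators may stop treatment at any time, and a patient must have three qualifying events to reach the gap in this row. All of that stands and limits the size of the point, but none of it supplies the missing dose.

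It can also be said that the missing rule may lie in the investigator's brochure or in the guidance that Section 4.2.2 cites. That is possible, so the point is confined to the visible text.

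Three stronger readings are tempting and should not be drawn.
- A reader might infer that sites will already differ at the first restart, at 2.0 or 1.5 mg/kg. At that restart only one dosing bullet in the row applies, and it orders a one-level reduction. Nothing in the row supports 2.0 mg/kg; that dose comes only by analogy with other tables or from the general same-level sentence. The firm gap in this row is at the third restart.
- A reader might try to count how many other rules can overrun the ladder on their own. The text does not support a firm count. Palmar-plantar erythrodysesthesia and blepharitis carry no occurrence limit in their own wording. But the former sits in the dermatologic section, whose Table 9 has limits, and the effusion rows have open-ended recurrence wording of their own.
- A reader might fear dosing during low platelets. The recovery requirement rules that out.

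**Conclusion.** The point holds: a stated dosing rule fails when followed. The grade 2/3 thrombocytopenia row orders three reductions against two available, so the third of its three permitted restarts has no dose, at infusion 4 of 8 at the earliest. Combined toxicities can reach the same gap by infusion 3. The grade 4 neutropenia and grade 4 thrombocytopenia rows contradict themselves, with 1.5 or 1.0 mg/kg possible for a patient coming from 2.0.

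The documents available here give no incidence for these sequences and none is assumed. Few patients are likely to be affected, and each is 1 of at most 17 (1/17 = 6%). The effect is on the safety and consistency of re-dosing. Sample size, type I error and power are unchanged. The conclusion rests on the visible protocol and would need revisiting if the investigator's brochure sets a dose floor. This should be corrected, but it does not threaten the trial's primary analysis.

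**What to change.** 1. Beside Table 4, add: *If a reduction below 1.0 mg/kg is required, permanently discontinue MGC018.*
2. In the grade 2/3 thrombocytopenia row, choose one occurrence rule that fits the ladder.
   - **Option A**, as in the grade 3 neutropenia row: restart on recovery to grade 1 or better, reduce one level after each of the first two occurrences, discontinue after the third. This keeps the first-event reduction already written and is the more cautious. The restart bullet must lose its own reduction, or the instruction is duplicated.
   - **Option B**, as in the six grade 2 rows: no reduction after the first occurrence, one level after each of the second and third, discontinue after the fourth. Because this row also covers grade 3, a first grade 3 event would then restart at an unreduced dose.
   
   The choice is clinical and belongs to the sponsor.
3. In each of the two grade 4 hematologic rows, keep one reduction instruction. Two levels matches the other seven grade 4 rows. Combined with item 1, it would stop a Level -1 patient at a first grade 4 event, so the sponsor should choose knowingly.

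The same amendment is a convenient place to reconcile Section 4.2.2 with Table 4 and correct its cross-references.

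**Cost.** One sentence, three bullets under Option A, and one bullet in each grade 4 row, with no change to design or analysis. A few heavily reduced patients would stop instead of staying at 1.0 mg/kg. Under Option A, a patient with repeated grade 2 thrombocytopenia would stop at the third occurrence instead of the fourth.

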4.2.2.1 MGC018

MGC018 will be administered by IV infusion at a dose of 2.0 mg/kg on Day 1 of each 28-day cycle until completion of cycle 8, unacceptable toxicity, or loss of clinical benefit as determined by the investigator after an integrated assessment of radiographic and biochemical data, local biopsy results (if available), and clinical status (see Section 3.1.1 for details). For subjects weighing ≥ 100 kg the doses will be based on 100 kg for these subjects. To decrease the frequency and severity of palmar-plantar erythrodysesthesia (PPE) and effusions, prednisone 40 mg will be given twice daily for three days of each cycle starting the evening after each infusion for a total of 6 doses. In addition, patients will be provided with a strong or moderate-strength topical steroid cream to be applied as prescribed to the hands and soles prophylactically for the first 12 weeks of therapy.

Administration of MGC018 will be performed in a monitored setting where there is immediate access to trained personnel and adequate equipment and medicine to manage potentially serious reactions. For anaphylaxis precautions, see Appendix 3. MGC018 infusions will be administered per the instructions outlined in Table 3.

Table 3. Administration of first and subsequent MGC018 infusions

| Study Drug | First Infusion | Subsequent Infusions |
|-----------------|---|--|
| MGC018 infusion | 
Premedication with acetaminophen (650mg to 1000 mg), diphenhydramine 50 mg PO or IV, famotidine 40 mg PO or 20 mg IV, and corticosteroid (e.g | 
If the patient experienced an infusion-related reaction (IRR) with any previous infusion, additional premedication may also be considered. |

| | | |
|---|---|---|

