| Pleural Effusion, Grade 4 | 
• Permanently discontinue MGC018• Recommend hospitalization with pulmonary consultation and diagnostic evaluation including chest X-ray and CT scan.• Initiate maximal supportive care including IV corticosteroids. Continue IV methylprednisolone 2 mg/kg/day for 5 days then switch to oral prednisolone 1 mg/kg/day x 3 days, then reduce to 60 mg/day prednisolone. Reduce prednisolone dose by 10 mg every 5-7 days (as toxicity allows) until dose is 10 mg/day. Once steroid dose is 10 mg/day, reduce by 5 mg every 5-7 days then stop. High doses may be used in consultation with the sponsor's medical monitor. |

Table 15. Management Guidelines for Pericardial Effusions

| Event | Management |
|-------------------------------|--|
| Pericardial Effusion, Grade 1 | 
 • No specific therapy required • Continue MGC018 |
| Pericardial Effusion, Grade 2 | 
 • Hold MGC018 • Consider diuretics • Consider corticosteroids: 1 to 2 mg/kg of oral prednisone or equivalent per day divided twice daily. Taper corticosteroids over 4 weeks or as clinically indicated • Resume MGC018 at next scheduled dose with a one level dose reduction if pericardial effusion resolves to \leq grade 1 within 21 days. If pericardial effusion grade 2 recurs further dose reduce by one level. |
| Pericardial Effusion, Grade 3 | 
 • Hold MGC018 • Consider pericardiocentesis. • Consider corticosteroids: 1 to 2 mg/kg of oral prednisone or equivalent per day divided twice daily. Taper corticosteroids over 4 weeks or as clinically indicated. • Resume MGC018 at next scheduled dose with a one level dose reduction if pericardial effusion resolves to \leq grade 1 within 21 days. If pericardial effusion grade 3 recurs further reduce dose by one dose level. |

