| Pericardial Effusion, Grade 4 | 
 • Permanently discontinue MGC018 • Hospitalize, consider pericardiocentesis • Recommend cardiology consult/diagnostic evaluation including echocardiogram • Initiate maximal supportive care including IV corticosteroids. Continue IV methylprednisolone 2 mg/kg/day for 5 days then switch to oral prednisolone 1 mg/kg/day x 3 days, then reduce to 60 mg/day prednisolone. Reduce prednisolone dose by 10 mg every 5-7 days (as toxicity allows) until dose is 10 mg/day. Once steroid dose is 10 mg/day, reduce by 5 mg every 5-7 days then stop. High doses may be used in consultation with the sponsor's medical monitor. |

NERVOUS SYSTEM EVENTS

Management guidelines for patients experiencing nervous system toxicity are provided in Table 16.

Table 16. Management Guidelines for Nervous System Events

| Event | Management |
|--------------|---|
| Grade 1 | 
• No specific therapy required, close monitoring of neuropathy |
| Grade 2 | 
• Hold MGC018• Consider neurology consultation• Consider corticosteroids: 1 to 2 mg/kg of oral prednisone or equivalent per day divided twice daily. Taper corticosteroids over 4 weeks or as clinically indicated.• Resume MGC018 at next scheduled dose if symptoms resolve to \leq grade 1 within 21 days with or without treatment. |
| Grade 3 or 4 | 
• Permanently discontinue MGC018• Consider hospitalization and neurology consultation• Begin corticosteroids 2 to 4 mg/kg of oral or IV methylprednisolone or equivalent per day divided twice daily. Continue IV methylprednisolone 2 mg/kg/day for a total of 5 days then switch to oral prednisolone 1 mg/kg/day x 3 days, then reduce to 60 mg/day prednisolone. Reduce prednisolone dose by 10 mg every 7 days (as toxicity allows) until dose is 10 mg/day. Once steroid dose is 10 mg/day, reduce by 5 mg every 5-7 days then stop |

CARDIOVASCULAR EVENTS

Management guidelines for patients experiencing cardiovascular toxicity are provided in Table 17.

Table 17. Management Guidelines for Cardiovascular System Events

| Event | Management |
|--------------|--|
| Grade 1 | 
 No specific therapy required; close monitoring |

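### In Tables 14 to 18 the steroid taper step worded as a reduction, from 1 mg/kg/day to a flat 60 mg/day, is a reduction only in patients above 60 kg

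*Combined protocol and SAP*

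**What the plan says.** Section 4.2.3.2 sets out toxicity management by organ system. Table numbers here follow the body of the protocol; the list of tables at the front numbers pleural effusions as Table 15.

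Five tables share one steroid schedule:

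- Table 14, pleural effusions, grade 4
- Table 15, pericardial effusions, grade 4
- Table 16, nervous system events, grade 3 or 4
- Table 17, cardiovascular events, grade 3 or 4
- Table 18, musculoskeletal events, grade 3, with grade 4 managed the same way

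In Tables 14 and 15 the schedule reads "Continue IV methylprednisolone 2 mg/kg/day for 5 days"; Tables 16 to 18 give the same daily dose for five days in total. All five then continue: "then switch to oral prednisolone 1 mg/kg/day x 3 days, then reduce to 60 mg/day prednisolone". After that the dose falls in 10 mg decrements to 10 mg/day and then in 5 mg decrements to zero. The interval for the 10 mg decrements is 5 to 7 days in Tables 14, 15, 17 and 18, but Table 16 differs: "then reduce to 60 mg/day prednisolone. Reduce prednisolone dose by 10 mg every 7 days (as toxicity allows) until dose is 10 mg/day".

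The only body-weight rule found is in section 4.2.2.1 and concerns the study drug: "For subjects weighing ≥ 100 kg the doses will be based on 100 kg for these subjects". The eligibility criteria set no minimum weight.

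**The concern.** The schedule passes from a weight-based dose to a fixed dose of the same drug by the same route, and calls the move a reduction. That word is true only over part of the weight range. For a patient below 60 kg the instruction gives a number and a direction that disagree. A site must either follow the number, and give more than on the previous day, or follow the direction, and leave the number. The rows concern the most severe events in their tables, and the study is multi-center with four named sites, so two sites could read the same sentence differently.

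**Working it through.** **Inputs.** Dose before the step: 1 mg/kg/day oral prednisolone for 3 days. Dose after the step: 60 mg/day oral prednisolone. Both are from Tables 14 to 18. The IV dose before the oral switch is methylprednisolone 2 mg/kg/day. Body weight W is in kg. The documents give no weight distribution, so the weights below are assumptions chosen to show the range.

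**The plan's own figure.** The protocol gives no derivation for 60 mg/day. It equals 1 mg/kg/day at one weight only: 60 / 1 = 60 kg.

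**Change at the step.** Change in mg/day = 60 − 1 × W. Relative change = (60 − W) / W.

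| W (kg) | Before (mg/day) | After (mg/day) | Change (mg/day) | Relative change |
|---|---|---|---|---|
| 40 | 40 | 60 | +20 | +50% |
| 45 | 45 | 60 | +15 | +33% |
| 50 | 50 | 60 | +10 | +20% |
| 55 | 55 | 60 | +5 | +9% |
| 60 | 60 | 60 | 0 | 0% |
| 70 | 70 | 60 | −10 | −14% |
| 80 | 80 | 60 | −20 | −25% |
| 100 | 100 | 60 | −40 | −40% |

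The sign changes at exactly 60 kg.

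**Comparison with the IV course.** The flat dose is numerically below the IV dose when 60 < 2 × W, that is, when W > 30 kg. At 50 kg the sequence is 100 mg/day IV, 50 mg/day oral, then 60 mg/day oral. The IV and oral drugs differ and no potency conversion is applied, so this compares milligrams only.

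**Search for a resolving clause.**

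- None of the five rows carries a weight condition or an alternative for lighter patients.
- The tolerance proviso in the schedule attaches to the later 10 mg decrements, not to the step to 60 mg/day.
- The permission for high doses after consulting the medical monitor appears only in Tables 14 and 15. It does not turn a routine increase into a reduction.
- The 100 kg rule covers MGC018, and at that weight the steroid step is a decrease in any case.
- The grade 2 rows of these tables and the grade 3 effusion rows let the clinician taper over 4 weeks or as the clinical picture requires. The five rows at issue set out fixed steps without that latitude.

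**The case against.** The other side has good points about reach, and most of them stand.

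*Guidelines, not fixed orders.* The tables are called guidelines, and the text introducing the effusion tables defers to institutional supportive care. Some variation between sites is therefore already accepted. This softens the consequence but does not remove the conflict in wording, and Tables 16 to 18 have no institutional-practice clause.

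*Few patients.* The trial enrolls up to 17. The problem needs someone under 60 kg with one of these severe events, and the documents give neither weights nor event rates for that subset. In Tables 14 to 17 MGC018 is already permanently discontinued in these rows, so re-dosing is not affected there. This stands.

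Three stronger readings are tempting but not supported:

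- A reader might infer that lighter patients receive more steroid than at any earlier point. They do not: above 30 kg the flat dose is numerically below the IV dose. The rise is relative to the 3-day oral step alone.
- A reader might infer a longer taper in lighter patients. Within each table the scheduled calendar from the IV course onward is the same at every weight.
- A reader might infer that the problem covers all effusions that count as adverse events of special interest. Section 5.2.3 lists grade 3 or higher, but this taper sits only in the grade 4 effusion rows. Section 5.2.3 does not name nervous system, cardiovascular or musculoskeletal events as such.

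Nor is the surrounding text the same in all five tables. The disputed step is, but the later interval in Table 16 is not.

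**Conclusion.** The point holds in limited form. In five tables, one taper step contradicts its own description for every patient below 60 kg and changes nothing at 60 kg. Relative to the preceding oral dose, the rise is 9% at 55 kg and 20% at 50 kg, reaching 50% only at an illustrative extreme of 40 kg. The threshold follows from the protocol's figures and needs no assumption. The number of patients affected cannot be stated and may be small or zero. The sample size, type I error and primary analysis are untouched. It merits correction because the text is unclear where severe toxicity is being managed and the correction is cheap.

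**What to change.** In Tables 14 to 18, the sponsor should reconcile three elements: the weight-based oral step, the flat step that follows it, and the word *reduce*. The sponsor should also confirm whether the later interval in Table 16 (every 7 days, against 5 to 7 days in the other four tables) is intended, so that an edit to the shared sentence does not alter it unnoticed. Which figures and which taper are right is for the sponsor and its medical monitor; none is proposed here.

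The cost is one sentence in each of five tables. Visits, sample size and analysis do not change.
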